1.4 Benefit/risk and ethical assessment

In clinical trials to date, AZD4901 has been well tolerated and dose escalations have been driven by the effects on testosterone levels that are now a key marker for efficacy in this new development. Nonclinical data indicate a potential for hepatotoxicity, but this has not been observed in the clinical program to date and patient's liver function will be monitored during their participation in the current trial.

AZD4901 may have the potential to induce and also inhibit *CYP3A4/5* enzymes. Due to the potential CYP induction/inhibition risk, concomitant use of AZD4901 with narrow therapeutic index drugs that are metabolised by *CYP3A4/5* should be avoided. Investigators should be aware that the exposure of other drugs metabolised by *CYP3A4* could be altered. See [Table 3](#) for a list of restricted medications.

As a disease of younger females, the patients in the trial are necessarily of childbearing potential, although PCOS often impairs fertility. Patients will be required to use reliable contraception throughout the trial. Hormonal contraception is disallowed as it could impact the primary efficacy measurements.

Polycystic ovary syndrome can result in disruption of menstruation, infertility, virilisation, and, in the longer term, serious metabolic consequences. Treatments are available, but are intended to suppress symptoms of PCOS with variable effectiveness. AZD4901 represents a possibility to effect the underlying biology of PCOS and this study is the first step to validate that hypothesis. As such, the benefit:risk is positive and administration of AZD4901 to women with PCOS is justified.

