4. SUBJECT SELECTION CRITERIA

The Investigator should keep a record, the patient screening log, of patients who entered prestudy screening.

Each patient should meet all of the inclusion criteria and none of the exclusion criteria for this study. Under no circumstances can there be exceptions to this rule.

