4.1 Inclusion criteria

For inclusion in the study, patients should fulfil the following criteria:

1. Provision of signed and dated, informed consent prior to any study specific procedures

2. Female patients between the ages of 18 to 45 years (inclusive) with suitable veins for cannulation or repeated venipuncture
3. A diagnosis of polycystic ovary disease; patient must fulfil all of the following criteria:
 - Polycystic ovaries (previously documented ultrasound from records are acceptable)
 - Free testosterone at screening greater than 85% of the age-specific upper limit of normal (ULN) as specified in [Appendix I](#)
 - Total testosterone < 5 nmol/L at screening
4. Amenorrhea or oligomenorrhea (defined as ≤ 6 menses per year)
5. Body mass index (BMI) between 18 and 40 kg/m² (inclusive)
6. Females must have a negative serum pregnancy test at screening and a negative urine pregnancy test before randomisation, must not be breast-feeding, must not have been pregnant within the 6 months prior to screening, and must not expect to conceive within the projected duration of the study
7. Patient is permanently or surgically sterilised or practices abstinence as a lifestyle choice, or who agrees to use/have their partner use effective methods of birth control for the duration of their study participation

Permanent sterilisation includes bilateral salpingectomy but excludes bilateral tubal occlusion. Effective methods of birth control within the study treatment period are defined as partner use of male condom plus one of the following: spermicide, vasectomy, tubal occlusion, or an intrauterine device that does not contain steroid hormones.

For inclusion in the optional genetic component of the study:

8. Provision of signed, written, and dated informed consent for optional genetic research. If a patient declines to participate in the genetic component of the study, the patient will not be excluded from the other aspects of the study.

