5. STUDY CONDUCT

5.1 Restrictions during the study

Patients will be required to:

1. Patients are to fast from 2 hours prior to the morning dose until 1 hour after dosing on Days 7 and 28.
2. Patients will be provided with a dosing diary to record the time they take their medication each day and symptom diary paper questionnaires to be completed every evening before bedtime.
3. Patients are to abstain from taking any medication (prescribed or over the counter products) except acetaminophen (up to 4 gram per day) or topical preparations, as specified in [Section 5.6](#), until completion of the follow-up visit.
4. Patients are to abstain from blood or plasma donation until 3 months after completion of the follow-up visit.
5. Patients are not to consume more than 3 alcoholic drinks per day from screening until completion of the final study visit.
6. Patients who are not permanently or surgically sterile must use effective non-hormonal methods of birth control, such as strict abstinence or use/have their partner use effective non-hormonal methods of birth control for the duration of their

study participation. Acceptable barrier methods of contraception include condom or occlusive cap (diaphragm or cervical/vault caps) with spermicidal foam/gel/film/cream/suppository.

7. Any intake of grapefruit, Seville oranges, or products containing grapefruit or Seville oranges, within 7 days of the first administration of IP and through duration of IP administration is not permitted.
8. Patients should not increase level of strenuous exercise or increase caffeine intake during participation in the study.

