5.2 Subject enrolment, randomisation, and initiation of investigational product

The Investigator will:

1. Obtain signed informed consent from the potential patient before any study specific procedures are performed
2. Assign potential patient a unique enrolment number, beginning with 'EXXX1001', where 'XXX' represents the site number
3. Determine patient eligibility. See Section 4.1 and Section 4.2
4. Assign eligible patient a unique randomisation code (patient number), beginning with '1001'

If a patient withdraws from participation in the study, then her enrolment/randomisation code cannot be reused.

Procedures for randomisation

Fifty-six patients (14 patients per treatment group) with PCOS will be randomly assigned to 1 of 4 treatment groups to have approximately 12 evaluable patients in each treatment group. A randomization scheme will be produced by _____ using the AstraZeneca Global Randomisation system.

Randomisation codes will be assigned strictly sequentially as patients become eligible for randomisation. If a patient withdraws from participation in the study, then her enrolment/randomisation code will not be reused. Any replacement patients will be assigned to the same treatment as the patient they are replacing, and adding 100 to the original randomisation code.

5.3 Procedures for handling subjects incorrectly enrolled, randomised, or initiated on investigational product

Patients who fail to meet the inclusion/exclusion criteria should not, under any circumstances, be enrolled or receive IP. There can be no exceptions to this rule. Patients

who are incorrectly enrolled, but are not yet randomised or initiated on treatment, should be withdrawn from the study.

Where patients who do not meet the inclusion criteria are enrolled in error or incorrectly started on treatment, or where patients subsequently fail to meet the study criteria post-initiation, the Investigator should inform the AstraZeneca Clinical Pharmacology Alliance (CPA) Physician immediately. The AstraZeneca CPA Physician must ensure all such contacts are appropriately documented.

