5.5.2 Doses and treatment regimens

At Visit 2, eligible patients will be randomly assigned to 1 of 4 treatment groups as below.

The IP will be administered as two AZD4901 and/or placebo tablets twice daily from Day 1 through the morning dose on Day 28, as follows:

- 20 mg AZD4901 once daily: one 20-mg AZD4901 tablet and 1 placebo tablet for the morning dose and 2 placebo tablets for the evening dose
- 20 mg AZD4901 twice daily: one 20-mg AZD4901 tablet and 1 placebo tablet for both the morning and evening doses
- 40 mg AZD4901 twice daily: two 20-mg AZD4901 tablets for both the morning and evening doses
- Placebo: two matching placebo tablets for both the morning and evening doses

Patients will be required to fast from 2 hours prior to the morning dose until 1 hour postdose on Days 7 and 28.

On Days 7 and 28, the morning dose of IP will be administered in the clinic with 240 mL water. On Days 14 and 21, it is suggested patients take their morning dose of IP with sufficient water in the clinic; however, if this is not practical, dosing may occur at home with the patient reporting to the clinic later in the day for scheduled procedures. Otherwise, all doses are taken with sufficient water on an outpatient basis and recording of dates and times in the dosing diary. At each study visit, patients are to bring diaries and unused IP supplies for assessment of treatment compliance. At the last study visit, patients are to return any unused IP supplies.

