6.3.5 Laboratory safety assessment

Blood and urine samples for determination of clinical chemistry, haematology, and urinalysis will be taken at the times indicated in the Study Plan (see [Table 1](#) and [Table 2](#)). The date and time of collection for all laboratory tests will be recorded in the CRF. Safety laboratory variables to be measured are presented in [Table 4](#). Collection of the PD markers, LH, FSH, and testosterone, as well as the monitoring samples, are discussed in [Section 6.6](#). Sample collection for 4- β -hydroxy (OH) cholesterol and 6- β -OH testosterone is discussed in [Section 6.5](#).

Table 4 Safety laboratory variables

Haematology	Clinical Chemistry	Urinalysis
Haemoglobin	Albumin	Blood
Hematocrit ^a	Alkaline phosphatase	Glucose
Leucocyte count	ALT	Total protein
Leucocyte differential (absolute counts)	AST	
Platelet count	Total bilirubin	Alcohol screen ^b
HbA _{1c}	Total calcium	Drug screen ^b
	Creatine kinase	Pregnancy test ^c
	Creatinine	
	Gamma-glutamyl transferase	
	Potassium	
	Sodium	
	T4 (total and free) ^d	
	Testosterone (total) ^d	
	TSH ^d	
	Serology screen ^e	
	Pregnancy test ^c	
	Prolactin ^d	

^a Performed only at screening, follow-up, and in the event of early termination.

^b Urine will be tested at the screening visit and on Day -1 for alcohol and the following drugs of abuse: amphetamines, barbiturates, tricyclic antidepressants, cocaine, methadone, morphine, 3,4-methylenedioxymethamphetamine (ecstasy), phencyclidine, tetrahydrocannabinol, and opiates. If a patient tests positive for drugs of abuse, a retest may be performed and she may be excluded from entering the study, as judged by the Investigator. Random urine drug and alcohol screens at subsequent visits may be performed at the discretion of the Investigator.

^c Serum pregnancy tests will be performed at screening; urine pregnancy tests will be performed at each subsequent visit.

^d Thyroid tests (TSH and total/free T4), total testosterone, and prolactin are collected at screening to determine study eligibility. See [Section 6.6](#) for additional information on thyroid, testosterone, and prolactin levels measured as part of the PD assessments.

^e Serology tests (HIV, hepatitis B, and hepatitis C) are performed at screening only.

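### Section 5.1 item 6 accepts an occlusive cap with spermicide during treatment, which inclusion criterion 7 does not

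*Protocol*

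**What the plan says.** Section 4.1, inclusion criterion 7, admits a patient who is permanently or surgically sterilised, who abstains as a lifestyle choice, or who agrees that she or her partner will use effective birth control while she is in the study. It then fixes what effective means: "Effective methods of birth control within the study treatment period are defined as partner use of male condom plus one of the following", followed by the list "spermicide, vasectomy, tubal occlusion, or an intrauterine device that does not contain steroid hormones". Diaphragms and cervical or vault caps are not in that list.

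Section 5.1 item 6 restates the duty as a restriction during the study. Patients who are not sterile must use effective non-hormonal contraception, which may be strict abstinence, throughout their participation. It then adds: "Acceptable barrier methods of contraception include condom or occlusive cap (diaphragm or cervical/vault caps) with spermicidal foam/gel/film/cream/suppository". It does not refer back to criterion 7.

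Three other statements bear on the point. Section 4 says of the entry criteria: "Under no circumstances can there be exceptions to this rule". Section 1.4 says that "the patients in the trial are necessarily of childbearing potential" and disallows hormonal contraception. Section 5.5.2 has patients take two "tablets twice daily from Day 1 through the morning dose on Day 28".

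**The concern.** Both texts apply to the days on which study drug is taken, and they disagree on whether a cap with spermicide is enough. Section 5.1 is where site staff would look for what a patient may and may not do once enrolled, and it names a method that the eligibility definition leaves out.

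At stake is pregnancy prevention during exposure to an investigational drug, in women who may not use hormonal contraception. Some will have stopped oral contraceptives to enter, since screening is set up to allow that washout, and will be choosing a new non-hormonal method. Item 6's list speaks to exactly that choice.

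**Working it through.** No plan figure is involved, so the check is a comparison of the two texts.

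**Step 1: do the rules cover the same time?** Item 6 runs for the whole of participation. Criterion 7 asks for agreement over the same span but limits its definition of effective methods to the study treatment period. Under Section 5.5.2, dosing runs from Day 1 to the morning of Day 28, nominally 28 − 1 + 1 = 28 calendar days. The overlap is certain for those days and is not established for screening or follow-up.

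**Step 2: which methods pass which rule during treatment?**

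| Method | Section 5.1 item 6 | Inclusion criterion 7 |
|---|---|---|
| Male condom plus spermicide | Accepted | Accepted |
| Cap or diaphragm plus spermicide, no condom | Accepted | Not accepted |
| Condom alone | Accepted only if the spermicide phrase belongs to the cap alone | Not accepted |
| Male condom plus vasectomy, tubal occlusion or non-hormonal IUD | Not named in the barrier list, but not ruled out | Accepted |

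The second row is a conflict on any reading. The third depends on how the sentence in item 6 is parsed. Sterilisation and abstinence lie outside the barrier list and are not part of this point.

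**Step 3: does anything else in the document resolve it?** Item 6 introduces its list with the word 'include', which leaves room for other methods but does not withdraw the cap. Section 1.4 asks only for reliable contraception without hormones. The Amendment 4 text shown changes the abbreviations and Sections 1.1.2, 1.4 and 5.6, and neither 4.1 nor 5.1. Contraception is not a matter that would be settled in a statistical analysis plan.

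**Step 4: what limits the consequence?** A woman who plans at entry to rely on a cap does not meet criterion 7 and should not be enrolled. After entry, Table 4 of Section 6.3.5 states that "urine pregnancy tests will be performed at each subsequent visit", and Section 13.3.1 requires drug to stop at pregnancy. These detect and shorten exposure; they do not prevent it.

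**Step 5: can the risk be sized?** No. The protocol does not say how many of the 56 patients might use a cap, and it gives no contraceptive failure rates and no reproductive-toxicity data.

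**The case against.** The strongest reply is that the stricter text already governs. Section 4 allows no exceptions, Section 5.2 sends the investigator to Sections 4.1 and 4.2 to determine eligibility, and item 6 itself asks for effective methods, a term that only criterion 7 defines. On this view a cap user never reaches dosing. The reply narrows the route to harm but does not close it: a patient may change method after entry, and a site may apply item 6 as it stands, because item 6 names the cap as acceptable without pointing to criterion 7.

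It is also fair to say that the sentence in Section 1.4 goes on to note that PCOS often impairs fertility, and that entry requires amenorrhoea or oligomenorrhoea and negative pregnancy tests. These lower the background chance of pregnancy. The protocol still requires contraception.

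A reader might infer that any patient using a cap automatically falls under Section 5.3, which covers cases "where patients subsequently fail to meet the study criteria post-initiation" and calls for immediate notice to the sponsor's physician. That is one reading only. Criterion 7 is met by agreeing to use effective methods, and the protocol does not say that a later change of method undoes it. A reader might also infer that patients are being told the wrong thing. Section 5.1 is addressed to sites, and the consent material is not in view.

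**Conclusion.** The inconsistency is real and stands in current text. During the treatment period, item 6 accepts a cap with spermicide, and possibly a condom alone, where criterion 7 requires a male condom plus a listed second method. It should be corrected because it concerns participant protection and the correction is small.

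Its reach is limited. It covers the dosing period, from Day 1 to the morning of Day 28. It affects patients who change method after entry and sites that work from item 6. Its probability and harm cannot be quantified from the protocol. The conclusion assumes that criterion 7 expresses the intended standard, which its closed definition and the no-exceptions rule support.

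A reader might go further and infer an effect on the pharmacodynamic analysis set, the variance or bias; nothing in the protocol supports that. Nor does the document show that criterion 7's definition was meant to govern screening and follow-up. A reader might also see a parallel contradiction in item 3 of Section 5.1, on concomitant medication. That item refers to Section 5.6, which holds the medication rules, so the two can largely be read together and it is not part of this finding.

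**What to change.** Keep the first sentence of Section 5.1 item 6. Replace its barrier-method list with: *During the study treatment period, effective methods are those defined in inclusion criterion 7.* A cap would then not be accepted without a male condom plus a listed second method, and the uncertainty about a condom alone would go as well. The replacement is deliberately limited to the treatment period; extending the definition to screening and follow-up would be a new policy, not an alignment.

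The cost is one sentence of amendment wording, any ethics committee approval required under Section 8.5, and a memo to sites. Any patient relying on a cap would have to change method. Sample size, visits and analysis are unaffected.

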5.2 Subject enrolment, randomisation, and initiation of investigational product

The Investigator will:

1. Obtain signed informed consent from the potential patient before any study specific procedures are performed
2. Assign potential patient a unique enrolment number, beginning with 'EXXX1001', where 'XXX' represents the site number
3. Determine patient eligibility. See Section 4.1 and Section 4.2
4. Assign eligible patient a unique randomisation code (patient number), beginning with '1001'

If a patient withdraws from participation in the study, then her enrolment/randomisation code cannot be reused.

Procedures for randomisation

Fifty-six patients (14 patients per treatment group) with PCOS will be randomly assigned to 1 of 4 treatment groups to have approximately 12 evaluable patients in each treatment group. A randomization scheme will be produced by _____ using the AstraZeneca Global Randomisation system.

Randomisation codes will be assigned strictly sequentially as patients become eligible for randomisation. If a patient withdraws from participation in the study, then her enrolment/randomisation code will not be reused. Any replacement patients will be assigned to the same treatment as the patient they are replacing, and adding 100 to the original randomisation code.

5.3 Procedures for handling subjects incorrectly enrolled, randomised, or initiated on investigational product

Patients who fail to meet the inclusion/exclusion criteria should not, under any circumstances, be enrolled or receive IP. There can be no exceptions to this rule. Patients

who are incorrectly enrolled, but are not yet randomised or initiated on treatment, should be withdrawn from the study.

Where patients who do not meet the inclusion criteria are enrolled in error or incorrectly started on treatment, or where patients subsequently fail to meet the study criteria post-initiation, the Investigator should inform the AstraZeneca Clinical Pharmacology Alliance (CPA) Physician immediately. The AstraZeneca CPA Physician must ensure all such contacts are appropriately documented.

5.4 Blinding and procedures for unblinding the study

5.4.1 Methods for ensuring blinding

In order to maintain study blinding, patients will be administered 2 AZD4901 and/or matching placebo tablets twice daily in a double-dummy design as described in Section 5.5.2.

Investigational product will be packaged for each patient as described in Section 5.5.1.

The following personnel will be unblinded as to the exact content of investigational treatments (ie, the randomization code):

- Personnel analyzing the PK samples

The randomization list will be kept in a secure location until the end of the study.

5.4.2 Methods for unblinding the study

Individual treatment codes, indicating the treatment randomisation for each randomised patient, will be available to the Investigator(s) or pharmacists at the study centre.

The treatment code should not be broken except in medical emergencies when the appropriate management of the patient requires knowledge of the treatment randomisation. The Investigator documents and reports the action to AstraZeneca, without revealing the treatment given to subject to the AstraZeneca staff.

AstraZeneca retains the right to break the code for serious AEs (SAEs) that are unexpected and are suspected to be causally related to an IP and that potentially require expedited reporting to regulatory authorities. Treatment codes will not be broken for the planned analyses of data until all decisions on the evaluability of the data from each individual patient have been made and documented. The interim administrative data review will be blinded to the study team.

5.5 Treatments

5.5.1 Identity of investigational product(s)

Investigational product	Dosage form and strength	Manufacturer
AZD4901	Plain, round, biconvex, white film-coated tablets, 20-mg	AstraZeneca
Placebo	Matching placebo tablets	AstraZeneca

Each patient will receive 1 box(es) for the morning doses and 1 box(es) for the evening doses. Each box will contain 2 bottles where the patient will take 1 tablet from each bottle at each dosing occasion. Bottles will be clearly labelled as to whether they are for morning or evening doses.

5.5.2 Doses and treatment regimens

At Visit 2, eligible patients will be randomly assigned to 1 of 4 treatment groups as below.

The IP will be administered as two AZD4901 and/or placebo tablets twice daily from Day 1 through the morning dose on Day 28, as follows:

- 20 mg AZD4901 once daily: one 20-mg AZD4901 tablet and 1 placebo tablet for the morning dose and 2 placebo tablets for the evening dose
- 20 mg AZD4901 twice daily: one 20-mg AZD4901 tablet and 1 placebo tablet for both the morning and evening doses
- 40 mg AZD4901 twice daily: two 20-mg AZD4901 tablets for both the morning and evening doses
- Placebo: two matching placebo tablets for both the morning and evening doses

Patients will be required to fast from 2 hours prior to the morning dose until 1 hour postdose on Days 7 and 28.

On Days 7 and 28, the morning dose of IP will be administered in the clinic with 240 mL water. On Days 14 and 21, it is suggested patients take their morning dose of IP with sufficient water in the clinic; however, if this is not practical, dosing may occur at home with the patient reporting to the clinic later in the day for scheduled procedures. Otherwise, all doses are taken with sufficient water on an outpatient basis and recording of dates and times in the dosing diary. At each study visit, patients are to bring diaries and unused IP supplies for assessment of treatment compliance. At the last study visit, patients are to return any unused IP supplies.

